8.1 Serious Adverse Events

A Serious Adverse Event (SAE) is any untoward medical occurrence that at any dose:

- results in death
- is life-threatening (defined as an event in which the subject was at risk of death at the time of the event; it does not refer to an event which hypothetically might have caused death if it were more severe)
- requires inpatient hospitalization or causes prolongation of existing hospitalization (see NOTE below)
- results in persistent or significant disability/incapacity
- is a congenital anomaly/birth defect
- is an important medical event (defined as a medical event(s) that may not be immediately life-threatening or result in death or hospitalization but, based upon appropriate medical and scientific judgment, may jeopardize the subject or may require intervention [eg, medical, surgical] to prevent one of the other serious outcomes listed in the definition above.) Examples of such events include, but are not limited to, intensive treatment in an emergency room or at home for allergic bronchospasm; blood dyscrasias or convulsions that do not result in hospitalization.) Potential drug induced liver injury (DILI) is also considered an important medical event. (See Section 6.6 for the definition of potential DILI.) Suspected transmission of an infectious agent (eg, pathogenic or nonpathogenic) via the study drug is an SAE.

Deaths due to disease progression will not be reported as an SAE.

Although pregnancy, overdose, cancer, and potential drug induced liver injury (DILI) are not always serious by regulatory definition, these events must be handled as SAEs.

Any component of a study endpoint that is considered related to study therapy (eg, death is an

endpoint, if death occurred due to anaphylaxis, anaphylaxis must be reported) should be reported as SAE.

NOTE:

The following hospitalizations are not considered SAEs:

- a visit to the emergency room or other hospital department < 24 hours, that does not result in admission (unless considered an important medical or life-threatening event)
- elective surgery, planned prior to signing consent
- admissions as per protocol for a planned medical/surgical procedure
- routine health assessment requiring admission for baseline/trending of health status (eg, routine colonoscopy)
- medical/surgical admission other than to remedy ill health and planned prior to entry into the study. Appropriate documentation is required in these cases
- admission encountered for another life circumstance that carries no bearing on health status and requires no medical/surgical intervention (eg, lack of housing, economic inadequacy, caregiver respite, family circumstances, administrative reason).
- Admission for administration of anticancer therapy in the absence of any other SAEs

8.1.1 Serious Adverse Event Collection and Reporting

Sections 5.6.1 and 5.6.2 in the Investigator Brochure (IB) represent the Reference Safety Information to determine expectedness of serious adverse events for expedited reporting. Following the subject's or the legal representative's written consent to participate in the study, all SAEs, whether related or not related to study drug, must be collected, including those thought to be associated with protocol-specified procedures. All SAEs must be collected that occur during the screening period and within 100 days of discontinuation of dosing. If applicable, SAEs must be collected that relate to any later protocol-specified procedure (eg. a follow-up skin biopsy).

The investigator should report any SAE that occurs after these time periods and that is believed to be related to study drug or protocol-specified procedure.

An SAE report should be completed for any event where doubt exists regarding its seriousness.

If the investigator believes that an SAE is not related to study drug, but is potentially related to the conditions of the study (such as withdrawal of previous therapy or a complication of a study procedure), the relationship should be specified in the narrative section of the SAE Report Form.

SAEs, whether related or not related to study drug, and pregnancies must be reported to BMS (or designee) within 24 hours. SAEs must be recorded on the SAE Report Form; pregnancies on a Pregnancy Surveillance Form (electronic or paper forms). The preferred method for SAE data reporting collection is through the eCRF. The paper SAE/pregnancy surveillance forms are only intended as a back-up option when the eCRF system is not functioning. In this case, the paper forms are to be transmitted via email or confirmed facsimile (fax) transmission to:

SAE Email Address: [contact]

SAE [contact]

For studies capturing SAEs/pregnancies through electronic data capture (EDC), electronic submission is the required method for reporting. The paper forms should be used and submitted immediately, only in the event the electronic system is unavailable for transmission. When paper forms are used, the original paper forms are to remain on site.

If only limited information is initially available, follow-up reports are required. (Note: Follow-up SAE reports should include the same investigator term(s) initially reported.)

If an ongoing SAE changes in its intensity or relationship to study drug or if new information becomes available, a follow-up SAE report should be sent within 24 hours to the BMS (or designee) using the same procedure used for transmitting the initial SAE report.

All SAEs should be followed to resolution or stabilization.

Any event that is both serious and unexpected must be reported to the Food and Drug Administration (FDA) as soon as possible and no later than 7 days (for a death or life-threatening event) or 15 days (for all other SAEs) after the investigator's or institution's initial receipt of the information. BMS will be provided with a simultaneous copy of all adverse events filed with the FDA.

SAEs should be reported on MedWatch Form 3500A, which can be accessed at:
<http://www.accessdata.fda.gov/scripts/medwatch/>.

MedWatch SAE forms should be sent to the FDA at:

MEDWATCH

[name]

[name]

Fax: [name] ([name])

<http://www.accessdata.fda.gov/scripts/medwatch/>

All SAEs should simultaneously be faxed or e-mailed to BMS at:

Global Pharmacovigilance & Epidemiology

Bristol-Myers Squibb Company

[contact]

Email: [contact]

- An SAE report should be completed for any event where doubt exists regarding its seriousness.
- For studies with long-term follow-up periods in which safety data are being reported, include the timing of SAE collection in the protocol.
- If the investigator believes that an SAE is not related to study drug, but is potentially related to the conditions of the study (such as withdrawal of previous therapy or a complication of a study procedure), the relationship should be specified in the narrative section of the SAE Report Form.
- If only limited information is initially available, follow-up reports are required. (Note:

Follow-up SAE reports should include the same investigator term(s) initially reported.)

- If an ongoing SAE changes in its intensity or relationship to study drug or if new information becomes available, a follow-up SAE report should be sent within 24 hours to BMS using the same procedure used for transmitting the initial SAE report. All SAEs should be followed to resolution or stabilization. All SAEs should be followed to resolution or stabilization.

8.2 Nonserious Adverse Events

A nonserious adverse event is an AE not classified as serious.

8.2.1 Nonserious Adverse Event Collection and Reporting

The collection of new nonserious AE information should begin at initiation of study drug and continue until 100 days from the last dose of study drug. Nonserious AEs should be followed to resolution or stabilization, or reported as SAEs if they become serious. Follow-up is also required for nonserious AEs that cause withholding or discontinuation of study drug and for those present at the end of study treatment as appropriate. All identified nonserious AEs must be recorded and described on the nonserious AE page of the CRF (paper or electronic).

Completion of supplemental CRFs may be requested for AEs and/or laboratory abnormalities that are reported/identified during the course of the study.

8.3 Laboratory Test Result Abnormalities

The following laboratory test result abnormalities should be captured on the nonserious AE CRF page or SAE Report Form (paper or electronic) as appropriate:

- Any laboratory test result that is clinically significant or meets the definition of an SAE
- Any laboratory test result abnormality that required the subject to have study drug omitted or discontinued
- Any laboratory test result abnormality that required the subject to receive specific corrective therapy.

It is expected that wherever possible, the clinical rather than laboratory term would be used by the reporting investigator (eg, anemia versus low hemoglobin value).

8.4 Pregnancy

If, following initiation of the study drug, it is subsequently discovered that a study subject is pregnant or may have been pregnant at the time of study exposure, including during at least 5 half lives after product administration, the investigator must immediately notify the BMS Medical Monitor/designee of this event and complete and forward a Pregnancy Surveillance Form to BMS Designee within 24 hours and in accordance with SAE reporting procedures.

In most cases, the study drug will be permanently discontinued in an appropriate manner (eg, dose tapering if necessary for subject safety).

In the rare event that the benefit of continuing study drug is thought to outweigh the risk, after consultation with BMS, the pregnant subject may continue study drug after a thorough discussion of benefits and risk with the subject

Protocol-required procedures for study discontinuation and follow-up must be performed on the

subject unless contraindicated by pregnancy (eg, x-ray studies). Other appropriate pregnancy follow-up procedures should be considered if indicated.

The investigator must immediately notify the BMS (or designee) Medical Monitor of this event and complete and forward a Pregnancy Surveillance Form to BMS (or designee) within 24 hours and in accordance with SAE reporting procedures.

Follow-up information regarding the course of the pregnancy, including perinatal and neonatal outcome and, where applicable, offspring information must be reported on the Pregnancy Surveillance Form.

Any pregnancy that occurs in a female partner of a male study participant should be reported to BMS. Information on this pregnancy will be collected on the Pregnancy Surveillance Form.

8.5 Overdose

All occurrences of overdose must be reported as SAEs.

8.6 Potential Drug Induced Liver Injury (DILI)

Wherever possible, timely confirmation of initial liver-related laboratory abnormalities should occur prior to the reporting of a potential DILI event. All occurrences of potential DILIs, meeting the defined criteria, must be reported as SAEs.

Potential drug induced liver injury is defined as:

AT (ALT or AST) elevation > 3 times ULN (5 x ULN in patients with liver metastasis) AND

Total bilirubin > 2 times ULN, without initial findings of cholestasis (elevated serum alkaline phosphatase),

AND

No other immediately apparent possible causes of AT elevation and hyperbilirubinemia, including, but not limited to, viral hepatitis, pre-existing chronic or acute liver disease, or the administration of other drug(s) known to be hepatotoxic.

8.7 Other Safety Considerations

Any significant worsening noted during interim or final physical examinations, electrocardiogram, x-ray filming, any other potential safety assessment required or not required by protocol should also be recorded as a nonserious or serious AE, as appropriate, and reported accordingly.

8.8 Protocol Monitoring Committee

A Protocol Monitoring Committee (PMC) will be established to provide oversight of safety and efficacy considerations in the protocol. The PMC meets monthly and reviews accrual, patterns and frequencies of all adverse events, protocol violations and when applicable, internal audit results.

9 STATISTICAL CONSIDERATIONS

9.1 Statistical Design

The result of Nivolumab alone clinical trial for virus-associated cancers including MCC is pending, but the estimated objective response rate with Nivolumab alone is estimated around 17% based on Avelumab and Pembrolizumab trial for patients without prior immunotherapy exposure or previously failed prior immunotherapy (refractory). Therefore, we will consider a 17% response rate as not warranting further study. We will use a 40% response rate as a promising result to pursue further study. In other words, we are interested in at least 23% improvement in treatment efficacy for either one of the two arms: Nivolumab + SBRT + Ipilimumab (Arm B) or Nivolumab + Ipilimumab (Arm A). Since both treatments are experimental therapy in this targeted population, Simon two-stage design is used to evaluate the treatment efficacy. To determine the best treatment arm, we utilize a Bayesian posterior probability with Simon two-stage design in a two-arm randomized trial in order to have objective comparison between the two arms¹¹⁰. This design has several unique features: (1) Randomization reduces selection bias and allows a greater degree of comparability, (2) The Simon two-stage design will allow for termination of an ineffective drug earlier when compared to historical control data, and (3) The Bayesian posterior probability provides additional power to detect a definitive differential treatment effect. This design has been employed in various lung cancer trials at Moffitt Cancer Center.

9.1.1 Sample Size Calculation

From historical data, we will consider 17% response rate as not warranting further study. We will use 40% response rate as a promising result to pursue further study. In other words, we are interested in at least 23% (40% vs. 17%) improvement in treatment efficacy for arms B versus A. For each arm, using a Simon Mini-Max two-stage design with 10% type I error rate and 10% type II error rate, 16 patients will be enrolled in the first stage of the trial. If 2 or fewer patients respond, the treatment will be stopped. If 3 or more patients show a response, 8 additional patients (a total of 24 patients per group) will be enrolled. If the total number responding is 6 or less, we will conclude that the treatment is not effective. If both arms fail at the first or second stage, the trial will stop. No winner will be claimed. The sample size will be 32 if both arms fail at the first stage and 40 if only one arm fails at the first stage. If only one arm pass the second stage, the arm will be the winner. If both arms pass the second stage, we will use the posterior probability, $Pr(B > A)$, (probability of the response rate in arm B higher than in arm A) to select the winner. A non-informative prior of beta distribution, beta(1,1) in both arms will be used to calculate the posterior probability. Arm B will be claimed as the winner if $Pr(B > A) > \delta = 0.8$.

Operating Characteristics

The operating characteristics of the design is evaluated by simulation (10000 times) using R software (www.r-project.org) with "clinfun" package. In particular, we are interested in the probability of (correctly) selecting an arm as superior to the other arm if it is truly superior, and conversely, the probability of (incorrectly) selecting an arm that is no better than the other arm.

Power Analysis

Power: Assuming that the true probabilities of response in arms B and A are 40% and 17%, respectively (scenario 1: 23% difference of response rate), the overall probability (power) of correctly choosing arm B as superior is 85% on the basis of superiority shown at the end of the trial.

The probability of stopping arm A early and declaring arm B superior at the end of the trial is 81%. There are 9% of both arms passing the second stage with 4% claiming arm B as the winner by the Bayesian posterior probability. In a 18% difference of response rate, the overall power is 74% and 77% for the comparison of arms B and A with 35% versus 17% (scenario 2) and 40% versus 22% (scenario 3), respectively. Proportion of both arms passing the 2nd stage is 8% in scenario 2 (scenario 3: 23%), with 2% (scenario 3: 10%) claiming arm B as the winner by the Bayesian posterior probability.

Type I error

Type I error: In the null hypothesis of a 17% response rate in both arms, there are 9% misclassifying arm B as winner (i.e., 9% type I error). Among them, only 1% has both arms passing the 2nd stage, and less than 0.01% misclassify arm B as winner.

Summary

Summary: With $\delta=0.8$, the design has a 85% power to detect a 23% difference of response rate. The power decreases to a range of 74-77% to differentiate a 18% difference of response rate. The type I error is controlled at 9% when both arms have a 17% response rate.

Tables of Power Analysis

Scenario 1: Arm B=0.4 versus Arm A=0.17 (Overall power of Arm B= 85%)

	B.fail.stage1	B.fail.stage2	B.pass
A.fail.stage1	0.01	0.04	0.42
A.fail.stage2	0.01	0.03	0.39
A.pass	0	0.01	0.09

Both arms passing the 2nd stage: 9%. Among them, Arm B claims 4.31% as winner

Overall power of Arm B= 85%

Scenario 2: Arm B=0.35 versus Arm A=0.17 (Overall power of Arm B= 74%)

	B.fail.stage1	B.fail.stage2	B.pass
A.fail.stage1	0.02	0.08	0.38
A.fail.stage2	0.02	0.07	0.33
A.pass	0	0.02	0.08

Both arms passing the 2nd stage: 8%. Among them, Arm B claims 2.33% as winner

Overall power of Arm B= 74%

Scenario 3: Arm B=0.4 versus Arm A=0.22 (Overall power of Arm B= 77%)

	B.fail.stage1	B.fail.stage2	B.pass
A.fail.stage1	0.01	0.03	0.25

A.fail.stage2	0.01	0.03	0.41
A.pass	0.01	0.02	0.23

Both arms passing the 2nd stage: 23%. Among them, Arm B claims 9.89% as winner

Overall power of Arm B= 77%

Scenario 4: Arm B=0.17 versus Arm A=0.17 (Type I error= 8.89%)

	B.fail.stage1	B.fail.stage2	B.pass
A.fail.stage1	0.22	0.2	0.04
A.fail.stage2	0.2	0.19	0.04
A.pass	0.05	0.04	0.01

Both arms passing the 2nd stage: 1%. Among them, Arm B claims 0.01% as winner

Type I error= 8.89%

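### Section 9.1.1 treats the historical 17% as Arm A's rate, so the Summary states power without naming Arm A's rate and shows the chance of wrongly selecting Arm B only at 17% in both arms

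*Combined protocol and SAP*

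**What the plan says.** Section 9.1 of the protocol estimates the response rate on nivolumab alone at about 17%, treats both trial arms as experimental, and seeks a gain of at least 23 points as an "improvement in treatment efficacy for either one of the two arms". Section 1.1 hypothesises that nivolumab plus ipilimumab, with or without SBRT, beats nivolumab alone, so Arm A is expected to improve as well.

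Section 9.1.1 sets the two benchmarks: "we will consider 17% response rate as not warranting further study", and "We will use 40% response rate as a promising result to pursue further study". It then describes the same 40% versus 17% as an "improvement in treatment efficacy for arms B versus A". The Statistical Considerations part of the Synopsis carries the same sentence.

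Under Operating Characteristics, Section 9.1.1 says two probabilities are of interest: choosing an arm that is truly better, and wrongly choosing one that is not. Four scenarios follow (Arm B / Arm A): 40/17, 35/17, 40/22 and 17/17. The Summary reports that "the design has a 85% power to detect a 23% difference of response rate", gives 74-77% for 18 points, and adds: "The type I error is controlled at 9% when both arms have a 17% response rate".

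**The concern.** The 17% changes meaning between Sections 9.1 and 9.1.1, from the rate on a historical comparator to the assumed rate in Arm A. The scenarios follow the second meaning, so none shows both arms active. That is the outcome Section 1.1 predicts, and the one in which the primary objective (Section 1.3.1, Arm A against Arm B) matters most.

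Two things follow. The Summary's power figures read as properties of a 23- or 18-point difference, although they also depend on where Arm A sits. And the wrong-selection probability that the plan says it wants is given at one equal rate only, the one at which both arms usually fail their own tests. A reader of a result naming Arm B the winner could attach an error of about 9% to it when both arms are active, and so credit SBRT with more certainty than the design gives.

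**Working it through.** **Inputs (Section 9.1.1).** Each arm is tested separately against 17%, "using a Simon Mini-Max two-stage design with 10% type I error rate and 10% type II error rate, 16 patients will be enrolled". At stage 1, "If 2 or fewer patients respond, the treatment will be stopped"; otherwise the arm goes to 24 patients and fails with 6 or fewer responders. If one arm passes, it wins. If both pass, Arm B wins when Pr(B>A) exceeds 0.8 under beta(1,1) priors.

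**Formulas.** With X1 ~ Bin(16, p) and X2 ~ Bin(8, p):

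- P(pass | p) = sum over x1 = 3 to 16 of P(X1 = x1) × P(X2 ≥ 7 − x1)
- P(name B) = P(B passes) × [1 − P(A passes)] + P(both pass and Pr(B>A) > 0.8)

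The posteriors are Beta(1 + x, 25 − x) with x responders of 24. For Arm A totals of 7 to 15, the 0.8 rule needs Arm B to lead by three responders. Everything is enumerated exactly, without simulation.

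**Pass probabilities.** 9.78% at p = 17%, 26.13% at 22%, 78.55% at 35%, 90.13% at 40%. The first and last agree with the stated 10% error rates.

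**The plan's own scenarios.**

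| B / A | B passes, A fails | both pass, B by the 0.8 rule | P(name B) | stated |
|---|---|---|---|---|
| 40 / 17 | 0.9013 × 0.9022 = 81.3% | 4.1% | 85.5% | 85% |
| 35 / 17 | 0.7855 × 0.9022 = 70.9% | 2.4% | 73.3% | 74% |
| 40 / 22 | 0.9013 × 0.7387 = 66.6% | 10.0% | 76.6% | 77% |
| 17 / 17 | 0.0978 × 0.9022 = 8.8% | 0.03% | 8.85% | 8.89% |

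All four reproduce within the error of 10,000 simulations. In the first row, 81.3 of the 85.5 points come from Arm A failing against history and only 4.1 from comparing the arms.

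**Equal arms at other rates.**

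| both arms at | B passes, A fails | 0.8 rule | P(name B) |
|---|---|---|---|
| 20% | 15.2% | 0.2% | 15.3% |
| 25% | 23.8% | 1.1% | 24.9% |
| 30% | 23.9% | 4.3% | 28.2% |
| 35% | 16.9% | 9.8% | 26.7% |
| 40% | 8.9% | 15.8% | 24.7% |
| 50% | 1.2% | 22.4% | 23.6% |

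Components are rounded separately. The largest value on a 2-point grid is at 30%. There, most of the error is Arm B passing while Arm A fails its own test by chance (23.9 of 28.2 points). By 40% most of it comes from the 0.8 rule (15.8 of 24.7 points).

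**Same differences, Arm A at 40%.**

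- 63 / 40 (23 points): 9.9% + 71.7% = 81.6%
- 58 / 40 (18 points): 9.9% + 60.8% = 70.6% (components rounded separately)

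With Arm A at 30% the corresponding figures are 82.6% (53 / 30) and 72.8% (48 / 30).

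**The case against.** The plan has a good deal on its side. Its figures are correct, each power figure is introduced with both arm rates in the prose and again in the scenario headings, and the 9% sentence carries its own condition. A reader might infer that the plan claims 9% for any pair of equal arms and is therefore wrong. The text does not support that: the condition of 17% in both arms appears in the Summary, in the Type I error paragraph and in Scenario 4. The fault is an omission, not a false statement or an arithmetic error.

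A reader might also infer that the design loses its power once Arm A is active. It does not. The loss is 85 − 81.6 = 3.4 points for a 23-point difference, and 3.4 to 6.4 points (74 or 77 minus 70.6) for an 18-point difference. Nor is it right that the posterior rule settles the matter whenever both arms are active; at 30% chance failure of Arm A dominates.

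Finally, this is a phase 2 design for picking a winner between two experimental arms. If both truly respond at 40%, naming Arm B does not advance an inactive regimen, and a wrong-selection chance near 25% may be acceptable. That stands. But the error would credit SBRT with a benefit it does not have, and a plan that accepts such a rate should state it.

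**Conclusion.** The point holds as a fault of labelling and reporting. Section 9.1.1 and the Synopsis attach 40% versus 17% to Arm B against Arm A, which conflicts with Sections 1.1 and 9.1, and the scenario set inherits that choice. The main consequence is the unreported chance of naming Arm B when the arms are equal: about 24-28% at true rates of 30-50%, roughly 2.7 to 3.2 times the 8.9% at 17%, and already 15.3% at 20%. The change in power is secondary.

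These results assume the stopping and selection rules exactly as written, full stage sizes of 16 and 24, independent arms, and that a 23- or 18-point difference with Arm A at 40% means Arm B at 63% or 58%. The documents do not give those two rates.

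**What to change.** 1. In Section 9.1.1 and the Synopsis, describe 17% to 40% as the gain of each arm over the historical nivolumab-alone rate.
2. Add scenario rows (Arm B / Arm A) at 30/30, 40/40, 63/40 and 58/40.
3. In the Summary, give both arm rates with every power figure: 85% at 40 versus 17, 74% at 35 versus 17, 77% at 40 versus 22, 82% at 63 versus 40, and 71% at 58 versus 40. Replacing 85% with a bare 82% would repeat the fault, because no single figure holds at every Arm A rate.
4. State that the 9% applies only at 17% in both arms, and that the chance of naming Arm B is about 24-28% when both truly respond at 30-50%.

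The cost is a few table rows and less favourable stated figures. No rule or sample size changes. Raising the 0.8 threshold is not a free alternative: at 0.9 the wrong-selection chance at 40/40 falls to 13.8%, but power falls to 62.5% at 63/40 and 48.9% at 58/40.

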1 INTRODUCTION AND STUDY RATIONALE

1.1 Research Hypothesis

Treatment with nivolumab and ipilimumab with or without SBRT will improve objective response rate when compared to nivolumab alone in subjects with metastatic Merkel cell carcinoma.

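### The stated 9% type I error covers only false wins by Arm B at 17%/17%; no error is given for two equally active arms (20–28%), and the 81% for early stopping of Arm A conflicts with the plan's own table (0.42)

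*Combined protocol and SAP*

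**What the plan says.** Each arm follows a Simon minimax two-stage design against a historical response rate of 17%. It stops with 2 or fewer responses in 16 patients, and fails with 6 or fewer in 24. Section 9.1 says "we are interested in at least 23% improvement in treatment efficacy for either one of the two arms". Section 9.1.1 adds that "If only one arm pass the second stage, the arm will be the winner". If both arms pass, B wins when Pr(B>A) exceeds 0.8 under beta(1,1) priors.

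The Operating Characteristics paragraph names the error of interest as "the probability of (incorrectly) selecting an arm that is no better than the other arm". The Type I error paragraph then reports that "there are 9% misclassifying arm B as winner (i.e., 9% type I error"), and the Summary states "The type I error is controlled at 9% when both arms have a 17% response rate". Of the four scenarios, only Scenario 4 (17%/17%) has equal rates.

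The Power Analysis paragraph for Scenario 1 (B 40%, A 17%) says: "The probability of stopping arm A early and declaring arm B superior at the end of the trial is 81" per cent.

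**The concern.** Four things do not line up.

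- **Event counted.** The plan names the wrongful selection of either arm as the error of interest but counts only false wins by B. The Scenario 4 table prints A's sole wins (0.05 and 0.04) without adding them in.
- **Null examined.** Section 1.3.1 makes A versus B the primary objective. Section 1.1 expects both regimens to beat the historical rate: "Treatment with nivolumab and ipilimumab with or without SBRT will improve objective response rate when compared to nivolumab alone". The plan's own power cases include "40% versus 22% (scenario 3"), with Arm A above 17%. For the question whether SBRT adds anything, the relevant null is therefore two arms with the same rate above 17%, and no such case is shown.
- **The 81%.** Stopping early most naturally means stopping after the first 16 patients. The Scenario 1 table gives about half of 81% for that.
- **Meaning of winner.** An arm that passes alone wins without any comparison with the other arm, although the power text speaks of superiority.

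A reader could take 9% as the chance of wrongly crediting SBRT with a benefit, and 81% as the chance that an inactive Arm A stops at stage 1 while B succeeds. Neither reading is correct.

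**Working it through.** **Inputs (Section 9.1.1).** n1 = 16, stop at ≤2; n = 24, fail at ≤6; beta(1,1) priors; threshold 0.8. The two arms are independent, and outcomes were enumerated exactly from binomial probabilities.

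**Per-arm probabilities.** With X1 ~ Bin(16, p) and X2 ~ Bin(8, p):

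- fail stage 1 = P(X1 ≤ 2)
- pass = P(X1 ≥ 3 and X1 + X2 ≥ 7)
- fail stage 2 = the remainder

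| p | fail stage 1 | fail stage 2 | pass |
|---|---|---|---|
| 0.17 | 0.4723 | 0.4299 | 0.0978 |
| 0.40 | 0.0183 | 0.0804 | 0.9013 |

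**Reproducing the plan.** P(B wins) = P(B passes) × P(A fails) + P(both pass and Pr(B>A) > 0.8).

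| Scenario (B/A) | exact | plan |
|---|---|---|
| 1: 40/17 | 0.8131 + 0.0414 = 85.5% | 85% |
| 2: 35/17 | 0.7087 + 0.0241 = 73.3% | 74% |
| 3: 40/22 | 0.6657 + 0.0999 = 76.6% | 77% |
| 4: 17/17 | 0.0882 + 0.0003 = 8.85% | 8.89% |

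The calculation matches the plan within simulation error (about 0.28 points for Scenario 4 at 10,000 runs).

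**Either-arm error at 17/17.**

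- B alone passes: 0.0978 × (1 − 0.0978) = 0.0882. A alone passes: the same.
- Both pass: 0.0978² = 0.0096. B wins by the posterior rule in 0.0003.
- No winner named when both pass and Pr(B>A) ≤ 0.8: 0.0882 + 0.0882 + 0.0003 = 17.7%.
- A named in that case: 1 − (1 − 0.0978)² = 18.6%.

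The plan's rounded Scenario 4 cells give 0.04 + 0.04 + 0.05 + 0.04 = 0.17 for the sole-passer part.

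**Equal rates above 17%.** Probability that B is declared winner:

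| common rate | B alone passes | both pass, posterior rule | B wins |
|---|---|---|---|
| 20% | 0.152 | 0.001 | 15.3% |
| 22% | 0.193 | 0.004 | 19.7% |
| 25% | 0.238 | 0.011 | 24.9% |
| 30% | 0.239 | 0.043 | 28.2% |
| 35% | 0.169 | 0.098 | 26.7% |
| 40% | 0.089 | 0.158 | 24.7% |
| 50% | 0.012 | 0.224 | 23.6% |

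The maximum is at about 30%. Below that the sole-passer route dominates; at 40% and above most false wins come from the 0.8 threshold.

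**The 81%.** In Scenario 1:

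- A stops at stage 1 and B passes: 0.4723 × 0.9013 = 0.426 (table: 0.42).
- A fails at stage 2 and B passes: 0.4299 × 0.9013 = 0.387 (table: 0.39).
- Sum: 0.813 (table: 0.42 + 0.39 = 0.81).

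So 81% is the probability that B passes and A fails at either stage.

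**Sole passer.** With 7/24 in B and 6/24 in A, B wins, but Pr(B>A) = 0.62. With 7/24 and 5/24 it is 0.74. Both are below the plan's own 0.8.

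**The case against.** The quoted sentence is true as written. It is conditional on 17% in both arms, and the preceding paragraph says that the event is a false win by B. The power figures and the posterior rule are also directed at B, so a B-directed error is coherent. A's chance of passing falsely is covered by the 10% per-arm type I error, and the Scenario 4 cells are printed. In a pick-the-winner phase 2 trial, choosing either of two truly active arms is not a false claim of activity, and rates above 40% are nowhere assumed in the plan. The 81% is a correct sum with the wrong label; power, sample size and decision rules do not depend on it.

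Much of this stands. The 9% is not a miscalculation, and the equal-rate figures answer a different null from 17%/17%. But the plan itself defines the error of interest for an arm without naming B, makes A versus B the primary objective and expects both arms to exceed the historical rate. A relaxed error may well be acceptable in such a design, but it can be judged only if it is shown. The equal-rate result also does not rest on rates above 40%: it is already 19.7% at 22%, the rate Scenario 3 uses for Arm A. The conflict between the 81% sentence and its table remains on the natural reading of early.

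**Conclusion.** The concern holds, as a fault in reporting and scope rather than in the 9% calculation itself.

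- The 9% is correct for false wins by B at 17%/17% (8.85%). The either-arm figure is about 18% (17.7–18.6%).
- The 9% does not bound the chance of wrongly preferring B when both arms are equally active. That chance is 20–28% at common rates of 22–50%, or two to three times the stated figure.
- The 81% sentence overstates early stopping of A with B passing nearly twofold (81% against 42.6%). The 85% power is unaffected.

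Two lesser points would not justify a change on their own: the plan names no outcome for A when both arms pass and Pr(B>A) is 0.8 or less, and sole-passer wins may be read as superiority.

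The figures assume independent arms, full accrual to 16 and 24 patients, and the rules as written. At equal rates above 17%, a false win means false superiority of B over A, not false activity against 17%.

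**What to change.** In Section 9.1.1, with matching synopsis wording where it applies:

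1. Label the 9% as the probability that B is falsely selected when both arms respond at 17%. Give the either-arm figure (17.7–18.6%) beside it, and state what is declared for A when both arms pass and Pr(B>A) is 0.8 or less.
2. Add equal-rate scenarios at 20, 22, 25, 30, 40 and 50%, and say that the 9% does not bound false preference for B above 17%.
3. Reword the 81% sentence: about 43% for A stopped at stage 1 with B passing, and 81% for A failing at either stage with B passing.
4. Report a sole passer as active against 17%, with Pr(B>A) beside it, rather than as shown superior to the other arm.

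The cost is text and a rerun of the existing simulation, plus a less favourable stated error. No patients are added, and neither the stopping rule nor B's winner rule changes.

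Extending the 0.8 requirement to a sole passer is possible but not needed. It would lower B's error at 17%/17% to 7.1% and its maximum over the rates examined to about 24%. Power in Scenarios 1, 2 and 3 would fall from 85.5, 73.3 and 76.6% to 81.7, 67.9 and 71.4%. It would change little at common rates of 40–50%.
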